12.4.3 Secondary Endpoint S3: Percent Responder at 1 year

This efficacy endpoint will be to characterize the responder rate at 1 year in all subjects treated with the Rezūm System. The endpoint is defined the same as the primary objective, but will be evaluated at 1 year of follow-up.

12.4.4 Secondary Endpoint S4: Percent Responder at 2 years

This efficacy endpoint will be to characterize the responder rate at 2 years in all subjects treated with the Rezūm System. The endpoint is defined the same as the primary objective, but will be evaluated at 2 years of follow-up.

12.4.5 Secondary Endpoint S5: Percent Responder at 3 years

This efficacy endpoint will be to characterize the responder rate at 3 years in all subjects treated with the Rezūm System. The endpoint is defined the same as the primary objective, but will be evaluated at 3 years of follow-up.

12.5 Ancillary Endpoints

The following ancillary endpoints are to provide additional characterization of the safety and effectiveness of the Rezūm System in the treatment of obstructive BPH.

12.5.1 Ancillary Endpoint A1: Additional Responder Analyses

A responder in this ancillary endpoint is defined as a subject who has an IPSS improvement >8 points post-treatment compared to baseline at each scheduled follow-up time point.

12.5.2 Ancillary Endpoint A2: Change in Qmax and PVR

The A2 efficacy endpoint is the changes in peak urinary flow rate (Qmax) and PVR compared to their baseline values at each scheduled follow-up time point.

12.5.3 Ancillary Endpoint A3: Change in Sexual Function

Changes in sexual function will be assessed using MSHQ-EjD and the IIEF questionnaires for changes in ejaculatory and sexual function.

12.5.4 Ancillary Endpoint A4: Change in Quality of Life

Quality of Life (QoL) changes will be measured using the QoL question in the IPSS and BPH Impact Index (BPHII) and EQ-5D (a standardized instrument for use as a measure of health outcome) assessment and also the average time before subjects was able to resume pre-treatment activity.

12.5.5 Ancillary Endpoint A5: Procedure Parameters

This includes:

- Procedure time
- Treatment time
- Percent of median lobe presented and treated

12.5.6 Ancillary Endpoint A6: PGI-I Questionnaire

This ancillary endpoint characterizes subjects' responses to the PGI-I, a single question transition scale asking the patient to rate their urinary tract condition now as compared with how it was prior to beginning treatment on a 7 point scale.

12.5.7 Ancillary Endpoint A7: Rezūm II Comparisons

This ancillary endpoint characterizes the similarity of outcomes between the 135 treatment arm subjects in the Rezūm II study with prostate sizes ≥ 30 cm³ and ≤ 80 cm³ treated with Rezūm and the Treatment group of the Rezūm XL study.

Time to first unplanned re-treatment will be compared between the Rezūm XL and Rezūm II subjects over 0-6 months. Additional time intervals may also be analyzed for comparison. The incidence of planned staging of treatment, where additional treatment is planned at the conclusion of the initial treatment procedure will be also be described for the Rezūm XL study.

Adverse event frequencies will be compared between Rezūm XL and Rezūm II subjects over 0-6 months post-procedure. Additional time intervals may also be analyzed for comparison.

12.6 Other Analyses

Adverse events, protocol deviations and device malfunction will be tabulated and included in the analysis. Descriptive statistics will be used in reporting these outcomes.

13 Definition of Study Success

The study will be declared a success if the primary efficacy and safety endpoints are met.

14 Definition of Adverse Event(s)

For purposes of this study, an AE is defined as any adverse change (i.e., *de novo* or preexisting condition) from the subject's baseline medical condition(s) occurring during the course of the study. For the purpose of AE documentation, the start of the study is defined as any time after the treatment has been initiated.

Subjects must be monitored from the start of the study, and throughout the duration of the study, for any and all AEs, including those observed as well as those reported by the subject. All AEs are to be documented by the investigator on the appropriate CRF. All AEs will remain under medical supervision until the Investigator deems the AE to be resolved, returned to baseline or stabilized at a new level no longer requiring medical supervision.

All AEs will be recorded in the CRF whether considered procedure-related or not, and will be classified as described in section 14.7.

Pre-existing conditions will not be reported as an AE unless there is an adverse change in that condition. Any AE which resolves and then recurs will be reported as a separate AE.

An AE may be volunteered spontaneously by the subject or discovered as a result of questioning or physical examination by an investigator or study staff.

14.1 Treatment Related Symptoms

The Rezūm procedure is designed to treat LUTS. Subjects to be treated have moderate-to-severe LUTS prior to treatment. These symptoms are expected to continue and may even worsen slightly prior to improvement as part of the healing process. All reported LUTS will be documented in the CRF. Other expected acute, but transient, worsening of symptoms from the treatment are dysuria, frequency of urination, urgency of urination, urge incontinence, hematuria, slowing of the urinary stream and acute retention as the tissue heals.

The classification of symptoms as an AE will be determined by the CEC.

14.2 Urinary Retention and Obstructive LUTS

14.2.1 Urinary Retention

Urinary retention is the inability to completely empty the bladder and can be acute or chronic.

There are many causations for urinary retention, but BPH in men over the age of 50 account for 53% of the incidence. Neurogenic spinal injury is common, acute prostatitis, medications and pelvic floor disturbance such as urinary external sphincter dyssynergia are other known causes.

Acute urinary retention happens suddenly and lasts only a short time. People with acute urinary retention cannot urinate at all, even though they have a full bladder requiring immediate emergency treatment (i.e., catheterization). Acute urinary retention is an anticipated thermal therapy effect of the Rezūm treatment.

Chronic urinary retention is more insidious and can occur gradually in men with bladder outlet obstruction leading to dysfunctional urinary detrusor with underactivity. This can occur silently over time and can lead to pyelocaliectasis, hydronephrosis with renal insufficiency or failure, bladder and renal calculi and urinary tract infections, occasionally with urosepsis.

14.2.2 Obstructive LUTS

Obstructive LUTS has some symptoms similar to urinary retention. Obstructive LUTS usually is a chronic condition and is sometimes referred to as chronic urinary retention. Symptoms of obstructive LUTS are:

- Poor stream
- Hesitancy
- Terminal dribbling
- Incomplete voiding
- Overflow incontinence (occurs in chronic retention)

14.3 Anticipated Thermal Therapy Effects

14.3.1 Tissue Blanching, Edema and Erythema

Tissue blanching, edema and erythema in the urethral lining and prostatic tissue are anticipated thermal therapy effects from the treatment with the Rezūm delivery system. Any reported symptoms from these anticipated effects will be reported as Adverse Events on the Adverse Event CRF.

14.4 Potential Anticipated Adverse Events

Potential anticipated AEs are those that may occur in association with a BPH treatment or procedure, include those AEs listed below or reported in the literature associated with surgical or minimally invasive BPH procedures:

- Sepsis and infection
- Fever

- Perforation of urethra
- Perforation of adjacent organs including the rectum, bladder and GI tract
- Urinary symptoms and adverse events including:
 - Dysuria
 - Frequency
 - Urgency
 - Nocturia
 - Acute or Chronic urinary retention
 - Incontinence
 - Sensation of not emptying bladder completely
 - Urethral stricture
 - Urethritis
 - Irritative urinary symptom
 - Urethral injury causing false passage or adhesion
 - Urinary clot retention
 - Chronic pain in the pelvic area
 - Bladder spasm
 - Hematuria with or without clot in urethra
 - Discharge or cloudy urine
 - Discharge of tissue material during urination
 - Scarring of the urethral system
 - Urinary tract infection
- Abscess (prostatic, bladder, scrotal)
- Bladder problems or damage (reduced bladder sensation, spasms, bladder neck contracture, bladder neck stenosis, bladder neck mucosal sloughing)
- Bladder perforation or rupture
- Damage to the urethral system
- Prostate seroma
- Kidney compromise or failure
- Hydronephrosis
- Reproductive system disturbances such as infertility
- Prostate abnormalities and damage
- Rectal incontinence
- Rectal damage (including fistulas)
- Rectal stenosis
- Rectal, perineal findings
- Anal irritation
- Elevated PSA
- Nerve damage
- Weakness or numbness
- Abdominal or low back pain
- Flu-like symptoms
- Hematospermia
- Epididymitis

- Blood pressure change during therapy
- Arrhythmia
- Flank pain
- Blood loss (> 500 ml)
- Bowel irritation
- Erectile dysfunction
- Retrograde ejaculation or ejaculatory dysfunction
- Anejaculation
- Pressure sensation
- Prostatitis
- Adverse reaction to medication and anesthesia as listed in the labeling
- Low blood pressure (hypotension)
- High blood pressure (hypertension)
- Fainting, dizziness, or blurred vision (vasovagal reaction, syncope)

Other potential non-pelvic anticipated adverse events that may occur in this subject population are:

- Allergic reaction
- Fatigue
- Dyspnea
- Confusion
- Memory loss
- Swelling or bruising (edema, hematoma)
- Aneurysm – thoracic and cranial
- Low back pain
- Pneumonia
- Collapsed lung
- Pulmonary embolism
- Pneumothorax
- Upper respiratory disease
- Cough
- Sore throat
- Apnea
- Coughing up blood (hemoptysis)
- Choking (aspiration)
- Venous thrombosis
- Myocardial infarction, angina, ischemia
- Cardiac arrhythmia
- Stroke or transient ischemic attack
- Brain damage
- Headache
- Depression
- Perforation of or damage to the gastrointestinal tract
- Abdominal pain

- Constipation
- Nausea or vomiting
- Adverse reaction to medication

14.5 Definition of Serious Adverse Event(s)

An AE is considered to be an SAE if it resulted, or could result in, if not mitigated:

- Death;
- A life-threatening situation;
- Requires the subject to be hospitalized or prolongs an existing hospitalization;
- Persistent or significant disability/incapacity; or,
- Is considered an important medical event.

Important medical events that may not meet one of the above definitions could be considered SAEs if they jeopardize the health of the subject or require surgical intervention to prevent one of the outcomes listed above. An SAE may or may not be related to the study procedure.

Classification of an AE to an SAE will be decided by the CEC.

14.6 Unanticipated Adverse Device Effect(s) (UADE)

A UADE is any serious adverse effect on the health or safety of a subject, any life-threatening problem or death caused by, or associated with a device, if such effect, problem, or death was not previously identified in nature, severity, or degree of incidence in the investigational plan (e.g., ICF, Study Protocol, Instructions for Use (IFU), publications, etc.), or any other unanticipated serious problem associated with a device that relates to the rights, safety, or welfare of subjects.

If an UADE associated with the investigational device occurs, the investigator shall notify the Sponsor and the IRB/EC as soon as possible.

The Sponsor will investigate the event and notify the FDA and all other participating IRBs/EC and investigators. Should the Sponsor determine that an UADE presents an unreasonable risk to all participating subjects, the Sponsor will suspend the clinical investigation and notify all participating investigators, IRBs/ECs, the FDA, and any other country regulatory bodies.

14.7 Reporting of all Adverse Events

All AEs must be recorded on a CRF. All AEs also must be described by (a) duration (start and resolution dates); (b) adjudication for severity; (c) relationship to the study device; (d) action taken to resolve the event; (e) outcome of the event; and (f) whether or not such event is considered to have been serious (g) determination of single vs recurrent event. Additional information, such as procedural notes, treatment notes, or a signed clinical summary, may be required as supporting documentation for the reported AE.

During the study, all deaths must be reported to the Sponsor within the period outlined in Table 17-1. All deaths also should be reported on the End of Study CRF. A copy of the subject's death

records, medical records for the events that led to the subject's death, and a death certificate (if available) should be provided.

14.8 Relationship of AEs to the Rezūm Device

A description of how an AE relates to the study procedure will be reported on the Adverse Event CRF and be determined by the Investigator using the following definitions:

- **Definite:** The AE follows a reasonable temporal sequence from the time of the index procedure, which includes AEs that occur during the index procedure or during the follow-up period.
- **Probable:** The AE follows a reasonable temporal sequence from the time of the index procedure, and the possibility can be excluded that factors other than the index procedure, such as underlying disease, concomitant drugs, or concurrent treatment caused the AE.
- **Possible:** The AE follows a reasonable temporal sequence from the time of the index procedure and the possibility of index procedure involvement cannot be excluded. However, other factors such as underlying disease, concomitant medications, or concurrent treatment are presumable.
- **Unlikely:** The AE has an improbable temporal sequence from the time of the index procedure, or such AE can be reasonably explained by other factors, including underlying disease, concomitant medication, or concurrent treatment.
- **Not related:** The AE has no temporal sequence from the time of the index procedure, or it can be explained by other factors, including underlying disease, concomitant medication, or concurrent treatment.

Those SAEs that are possibly related to the device, the procedure, or the disease state being treated will be reviewed and adjudicated by the CEC. The CEC will review in tabular format all non-device/procedure/disease-related SAEs.

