19.1 Clinical Events Committee (CEC)

Evaluation and adjudication of safety data (e.g., SAEs, all deaths, etc.) will be performed on an ongoing basis by the CEC. This CEC will be comprised of three independent physician reviewers with an expertise in urology. Members of the CEC will not be participants in the study.

All reported adverse events that are possibly related to the device, the procedure, or disease state being treated will be reviewed and adjudicated by the CEC. The CEC will review in tabular format all non-device/procedure/disease-related events.

20 Study Contact

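### The relatedness grades in section 14.8 are out of order at the top and overlap at the bottom, so investigator labels and the triage of borderline events to full CEC adjudication are not reproducible

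*Combined protocol and SAP*

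**What the plan says.** Section 14.8 holds the only relatedness definitions in the documents, and the investigator applies them: "A description of how an AE relates to the study procedure will be reported on the Adverse Event CRF and be determined by the Investigator". The five grades are:

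- *Definite*: "The AE follows a reasonable temporal sequence from the time of the index procedure, which includes AEs that occur during the index procedure"; the sentence then adds the follow-up period. Other causes are not mentioned.
- *Probable*: the same timing, "and the possibility can be excluded that factors other than the index procedure" caused the event.
- *Possible*: the same timing, with involvement of the procedure not excluded. "However, other factors such as underlying disease, concomitant medications, or concurrent treatment are presumable".
- *Unlikely*: improbable timing, "or such AE can be reasonably explained by other factors".
- *Not related*: "The AE has no temporal sequence from the time of the index procedure, or it can be explained by other factors".

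Relatedness then governs what the CEC does, in two places. Section 14.8 sends for adjudication "Those SAEs that are possibly related to the device, the procedure" or the disease under treatment. Section 19.1 sends "All reported adverse events that are possibly related to the device, the procedure, or disease state being treated". Both leave the remainder to be reviewed as a table. Neither says which of the five grades count as possibly related.

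Three other sections bear on this. Section 14.7 asks for the relation to the study device. Section 12.2 defines a device-related composite and gives its event types to the CEC. Section 14.5 leaves it to the CEC to decide which AEs are serious.

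**The concern.** A causality scale works only if its grades are ordered and an event falls into one of them. Here two investigators who read the text literally can give the same event opposite labels, and both comply with the protocol.

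The trial has a single arm, so there is no concurrent control against which misattribution would show up. Section 9.3 intends the data to support a wider labelled indication. A table of related AEs is part of that evidence, and a reader would take its labels at face value.

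The triage matters most for late events. The last scheduled retroperitoneal ultrasound is at 6 weeks (Table 10-2, section 11.7), while the safety composite runs to 6 months (section 12.2). The independent reader's list in section 14.11 also omits Grade 2 hydronephrosis, one of the four composite components. Hydronephrosis that appears after 6 weeks would come to notice mainly through site AE reporting, where the site's own grade carries more weight.

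**Working it through.** **1. The grades side by side (section 14.8).**

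| Grade | Timing required | Condition on other causes |
|---|---|---|
| Definite | Reasonable | None |
| Probable | Reasonable | Must be excluded |
| Possible | Reasonable | Presumed; procedure not excluded |
| Unlikely | Improbable, *or* the next column suffices | A reasonable explanation exists |
| Not related | None, *or* the next column suffices | An explanation exists |

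**2. Order.** Every event that meets *Probable* also meets *Definite*, but not the reverse. *Probable* is the stricter subset, so the top two grades are inverted.

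**3. Overlap.** Take an event with reasonable timing, where the procedure cannot be excluded and another illness or drug could also account for it. It meets *Definite* (timing), *Possible* (timing, other factors presumed), *Unlikely* (reasonable other explanation) and *Not related* (other explanation). It fails only *Probable*. That is four of five grades for one event.

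**4. Effect on CEC triage.** Read *possibly related* in the natural way, as *Possible* or higher.

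- *Definite* and *Probable* both lie above the threshold, so exchanging them moves no event across it. A timing-only *Definite* can only send more events to the CEC.
- The event in step 3 can be placed above the threshold (*Possible*) or below it (*Unlikely*, *Not related*). The lower-grade overlap therefore leaves the triage open.
- Both triage sentences also admit events related to the disease being treated, so an event put down to BPH should still be adjudicated. The 14.8 scale has no grade for relation to disease, so the label does not record this. The events left to the table are those attributed to other illness, medication or concurrent treatment.

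**5. What is graded.** The heading of 14.8, item (c) of 14.7 and the composite in 12.2 all refer to the device. The definitions in 14.8 refer only to the study or index procedure. The documents give the CEC no separate relatedness definition.

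**6. The plan's own figure.** Inputs from section 12.2: n = 88, performance goal 12%, one-sided exact binomial test at 5%. The p-value with k events is P(X ≤ k) = Σ C(88, i) × 0.12^i × 0.88^(88−i), for i = 0 to k.

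- k = 5 (5/88 = 5.7%): 0.0393, below 0.05.
- k = 6 (6/88 = 6.8%): 0.0846, above 0.05.

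The stated limit of 5 subjects reproduces. None of its inputs comes from the 14.8 scale.

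**7. Other routes to the CEC.** Composite events are CEC-adjudicated (12.2) and stopping-rule events are CEC-determined (9.3.3). Cystoscopy recordings go to the CEC (11.4). New ultrasound abnormalities at 2 or 6 weeks get a final CEC ruling (11.7). An independent reader looks for unreported complications on the ultrasounds (14.11).

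**The case against.** The strongest reply is that the decisive analyses do not use the investigator's label. The composite and the stopping rule rest on the CEC, cystoscopy and ultrasound bring cases to it independently, and events called unrelated are still listed to it. That stands, and it confines the point to investigator labels, tables split by them, and borderline triage.

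The reply also limits several stronger readings that a reader might infer:

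- *That the inversion decides what the CEC adjudicates.* It does not, by step 4.
- *That any event with a disease explanation escapes adjudication.* Both triage sentences include the disease being treated.
- *That sections 14.8, 14.5 and 19.1 form a circle in which serious events are lost.* Section 19.1 covers all possibly related AEs and so contains the narrower 14.8 sentence. The two should match, but 19.1 already lets events reach the CEC before they are classed as serious.
- *That the comparison with Rezūm II (A7) is undermined.* Section 12.5.7 compares AE frequencies without restricting them to related events, and section 14 records all AEs whatever their relation.
- *That the related share could rise from 69% to 100%.* Table 8-9 gives (138 + 9)/(164 + 50) = 147/214 = 68.7% of non-serious treatment-arm events related over 0 to 12 months. Those are adjudicated Rezūm II data, on a relatedness scale the documents do not describe. Reaching 100% would need every follow-up event to have reasonable timing, which remains a judgement. The window is also selective: adding the 45 events at >12 to 24 months, none related, gives 147/259 = 56.8%. The table cannot size the effect here.

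One part of the reply is incomplete. Section 12.2 does not say that composite-type events go to the CEC whatever the site's label, and scheduled renal imaging stops at 6 weeks.

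**Conclusion.** The point holds as a defect in the text of section 14.8. The top two grades are in the wrong order, the lower three are not mutually exclusive, and the scale grades the procedure where 14.7 and 12.2 refer to the device. Investigator relatedness labels, and any table split by them, cannot be reproduced from the definitions. Which borderline events receive full adjudication is also left open.

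The size cannot be computed, because the documents hold no data on how investigators in this trial label events. No sample size, threshold or test changes. The documents do not support the inference that the primary safety result or the stopping rule is unreliable. The conclusion about triage assumes that *possibly related* means *Possible* or higher, which the protocol does not state.

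The text should be corrected: the definitions fail as written, and the remedy is cheap.

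**What to change.** Rewrite 14.8 as follows:

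1. *Definite*: reasonable timing and other causes excluded. *Probable*: reasonable timing and other causes unlikely. *Possible*: reasonable timing and other causes equally plausible.
2. Define *Unlikely* and *Not related* so that they exclude each other and exclude *Possible*.
3. State that *Possible* or higher counts as possibly related for CEC review.
4. Record relation to the device and relation to the procedure as separate items on the AE form.
5. Change the 14.8 review sentence to cover all AEs, as 19.1 does, and not only SAEs.
6. State that every event of a composite type goes to the CEC whatever the investigator's label, consistent with 12.2.

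The cost is protocol and CRF wording and slightly more CEC review.
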